### 4.3. Exclusion Criteria

Each patient must not meet any of the following exclusion criteria to be eligible for enrollment in the study:

1. Estimated Glomerular Filtration Rate  $< 20$  mL/min/1.73 m^2 (using the Modification of Diet in Renal Disease [MDRD] formula);
2. Uncontrolled hypertension;
3. Uncontrolled ischemic heart disease;
4. Uncontrolled clinically significant cardiac arrhythmia;
5. Untreated hypo- or hyperthyroidism;
6. Prior major organ transplant;
7. Known or suspected systemic bacterial, viral, parasitic, or fungal infection;
8. Seropositive for hepatitis B virus, hepatitis C virus (HCV) or known to be HIV positive;

9. Received an investigational agent other than tafamidis, diflunisal, doxycycline, or taurooursodeoxycholic acid, or an investigational device within 30 days prior to first dose of study drug;
10. Discontinued ALN-TTRSC-002 due to a treatment-related AE;
11. Metastatic cancer within the past 5 years;
12. Any conditions which, in the opinion of the Investigator, would make the patient unsuitable for enrollment or could interfere with the patient's participation in, or completion of, the study.
13. History of allergic reaction to an oligonucleotide or GalNAc.
14. Blinding Procedure

This is an open-label, multi-dose study; all patients will receive ALN-TTRSC. No blinding procedures are needed.

#### **4.4. Patient Withdrawal**

Patients are free to withdraw from the study at any time and for any reason, without penalty to their continuing medical care. For those patients who withdraw early, every effort should be made to complete the ET visit (see Section 4.4.2 for handling of patients who withdraw).

##### **4.4.1. Reasons for Withdrawal**

The Investigator or designee may withdraw a patient from the study if the patient:

- Is in violation of the protocol.
- Experiences a serious or intolerable AE.
- Becomes pregnant.
- Requests to be withdrawn from the study (patient withdrawal of consent).
- Is found to be considerably non-compliant with the protocol-required ALN-TTRSC dosing visits.

A patient may also be withdrawn from the study if, in the Investigator's opinion, he or she is unable to continue. The Investigator will also withdraw the patient from the study upon the request of Alnylam, including if Alnylam terminates the study. Upon occurrence of a serious or intolerable AE, the Investigator or designee will make every possible attempt to confer with Alnylam before discontinuing the patient.

Missing an occasional dose of study medication will not necessarily result in the patient being withdrawn from the study. However, if a patient misses 2 consecutive doses of study medication, the Investigator at the site and the Medical Monitor will discuss the appropriate management measures up to and including withdrawal from the study.

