b The End-of-study or ET visit is scheduled approximately 7 days following the last dose. The Follow-up visit is scheduled approximately 4 weeks following the End-of-study or ET visit, if applicable. Patients who discontinue early will be required to report to the clinic for an End of Study visit and a Follow-up visit. For patients who discontinue

early and have provided consent, overall health status will be documented by either telephone contact or non-patient contact follow-up (eg, medical record check) at time points corresponding to study Day 504 (Week 72), if applicable, and study Day 1344 (Week 192).

- c During the treatment period, doses will be administered weekly ( $\pm$  2 days). Doses may be administered at the clinical site or at home according to Section 5.5.
- d Subcutaneous injection of ALN-TTRSC into the abdomen. The upper arm or thigh may also be used (see the ALN-TTRSC Pharmacy Manual).
- e Assessment should be performed before dosing.
- f The pregnancy test will be performed for WOCBP only. A serum pregnancy test should be performed at Screening/Baseline. Urine pregnancy tests at other visits.
- g The serum creatinine values should be in mg/dL to 2 decimal places (e.g., 0.95 mg/dL) OR values in  $\mu$ mol/L to the nearest whole number (e.g., 84  $\mu$ mol/L) when calculating eGFR using the MDRD study equation; see <http://nkdep.nih.gov/lab-evaluation/gfr-calculators.shtml> for an eGFR calculator.
- h Vital sign measurements include blood pressure, pulse rate, oral body temperature, and respiratory rate. Vital signs will be measured manually in the supine position after the patient has rested comfortably for 10 minutes. Each patient's blood pressure should be taken using the same arm. Vital signs should be collected during any unscheduled clinic visit.
- i For the 12-Lead ECG, each lead shall be recorded for at least 3 beats at a speed of 25 mm/s. Triplicate recordings will be obtained. The electrophysiologic parameters assessed will be rhythm, ventricular rate, PR interval, QRS duration, QT interval, ST and T-waves and QTcB.
- j Coagulation studies include PT, aPTT, and INR and will be performed on all patients.
- k Blood samples for vitamin A will be analyzed by a central laboratory.
- l Refer to Table 4 for PK Sampling Schedule.

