### **2.2. Secondary Objectives**

Secondary objectives of this study are to assess the PD effect of long-term dosing of ALN-TTRSC on serum levels of TTR and the clinical effects of long-term dosing of ALN-TTRSC, including effect on mortality, hospitalization, and 6-MWT.

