**Dose-modification criteria:**

If a study drug-related AE occurs in a patient that the Investigator judges as presenting a potential risk to the patient for further dosing, the Medical Monitor and Investigator will review all available safety data for that patient and for all other patients enrolled in the study. Based on this review it may be decided to discontinue further administration of ALN-TTRSC, or, if the Investigator concurs, the patient may resume ALN-TTRSC at the same dose or, at a lower dose of 250 mg.

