### 7.2. Serious Adverse Event Definition

An SAE is any untoward medical occurrence that at any dose:

- Results in death;
- Is life-threatening (an event which places the patient at immediate risk of death from the event as it occurred. It does not include an event that had it occurred in a more severe form might have caused death);
- Requires inpatient hospitalization or prolongation of existing hospitalization;
- Results in persistent or significant disability/incapacity;
- Is a congenital anomaly or birth defect;
- An important medical event that may not be immediately life-threatening or result in death or hospitalization but may jeopardize the patient and may require intervention to prevent one of the other outcomes listed above. Examples of such events include allergic bronchospasm requiring intensive treatment in an emergency room or at home, blood dyscrasias, convulsions, or the development of drug dependency or abuse.

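### Section 4.4.1 allows withdrawal from the study, not only from drug, for any serious AE, and what is collected afterwards does not name hospitalizations or include further walk tests

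*Protocol*

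**What the plan says.** Section 4.4.1 of the Protocol opens its list of reasons with "The Investigator or designee may withdraw a patient from the study if the patient" meets any listed ground. One ground is "Experiences a serious or intolerable AE". It is not limited to events related to study drug. The same section asks that, on such an event, the Investigator or designee "will make every possible attempt to confer with Alnylam before discontinuing the patient".

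Section 7.2 counts as serious an untoward medical occurrence that "Requires inpatient hospitalization or prolongation of existing hospitalization". Section 2.2 sets as a secondary objective "the clinical effects of long-term dosing of ALN-TTRSC, including effect on mortality, hospitalization, and 6-MWT". Section 8.2.4 summarizes the frequency of all, cardiovascular and heart-failure hospitalizations, and the change in 6-MWT by time point.

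On what follows, Table 2 footnote b says: "Patients who discontinue early will be required to report to the clinic for an End of Study visit and a Follow-up visit". The same footnote, Table 1 footnote d and Section 4.4.2 add a contact by telephone or record check for consenting patients, to document overall health status. The footnotes time it at Day 504, if applicable, and Day 1344. Section 9.2.4 gives its purpose as limiting missing data. Section 6.4.9 ends AE collection at the Follow-up visit.

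Section 5.6 treats stopping drug separately: after a review of safety data "it may be decided to discontinue further administration of ALN-TTRSC". It does not say whether such a patient stays on study or on what visit schedule.

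**The concern.** A hospitalization is both an outcome to be counted and a listed reason for ending observation. The patients most exposed to the rule are those with serious events, who are also likely to be admitted again and to lose walking distance. If some of them leave the study, their later admissions and walk tests are not scheduled to be collected, and the loss depends on the outcome.

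Section 8.2.9 analyses data as reported, with no imputation unless specified, so late 6-MWT means would rest on those who remain. There is no control arm in which a similar loss would show, and Section 4.4.3 allows no replacements, so each patient lost is about 4% of the cohort (1/25). An analysis plan cannot recover data that were never collected, so the remedy belongs in the protocol.

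**Working it through.** The plan states no hospitalization rate, withdrawal probability or dropout allowance, so it has no figure of its own to reproduce. The check has three parts.

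**1. What remains after discontinuation**

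| Item | If the patient stays | If the patient discontinues early |
|---|---|---|
| 6-MWT | Days 168, 336, 504, 672, 840, 1008, 1176, 1344 (8 tests) | Tests already done, plus one at ET |
| Cardiac history review | Every 12 weeks | Those already done, plus one at ET |
| AEs, and so admissions | Through the Follow-up visit after Day 1344 | Through the Follow-up visit about 4 weeks after ET |
| Later contact | Not needed | Overall health status at Day 504 (if applicable) and Day 1344, with consent; hospitalizations not named |

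**2. Walk tests lost**

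Lost = 8 − (scheduled tests reached) − 1 at ET.

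- Withdrawal at Day 100: 8 − 0 − 1 = 7 lost.
- Withdrawal at Day 400: 8 − 2 − 1 = 5 lost.
- Withdrawal at Day 800: 8 − 4 − 1 = 3 lost.

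**3. Hospitalizations missed (illustration only)**

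Assume a constant rate L per patient-year, and a probability w that a hospitalization leads to withdrawal. Neither is in the Protocol. Follow-up is T = 1344/365.25 = 3.68 years. Death, and anything recovered through the later contacts, are ignored.

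- Expected per patient with full follow-up: L × T.
- Expected per patient captured: (1 − exp(−L × w × T)) / w.

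| L per year | Full | w = 0.10 | w = 0.25 | w = 0.50 |
|---|---|---|---|---|
| 0.2 | 0.74 | 0.71 (4% missed) | 0.67 (9%) | 0.62 (16%) |
| 0.5 | 1.84 | 1.68 (9%) | 1.47 (20%) | 1.20 (35%) |
| 1.0 | 3.68 | 3.08 (16%) | 2.41 (35%) | 1.68 (54%) |

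Death matters over this period. Section 1.1.2 gives median survival after diagnosis of about 3.5 years for two of the three cardiac forms it describes. As a rough check, assume exponential survival with that median, so the death hazard is m = ln 2/3.5 = 0.198 per year. Full follow-up then gives L(1 − exp(−mT))/m, and capture gives L(1 − exp(−(m + Lw)T))/(m + Lw).

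- L = 0.2, w = 0.1: 0.523 against 0.506, 3% missed.
- L = 1.0, w = 0.5: 2.61 against 1.32, 49% missed.

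The range narrows slightly, from 4–54% to 3–49%. These patients are already past diagnosis, so the survival input is itself only an assumption.

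**The case against.** The strongest reply is that the rule is permissive and the sponsor has already provided for missing data. Much of this stands. Section 4.4.1 says the Investigator may withdraw the patient, and the sponsor is to be consulted first where possible. Collection does not stop at the event: the ET visit includes a walk test and a cardiac review, AEs run to the Follow-up visit, and Section 7.5 follows serious AEs until resolved, chronic or stable. The later contacts could recover vital status and some admissions. The study is descriptive, has safety as its primary objective and enrols about 25 patients, so no test depends on these summaries.

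What does not stand is that this closes the gap. Consultation sets no limit on which serious AEs qualify. The contacts do not name hospitalizations, and neither a telephone call nor a record check can yield a walk test.

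Several stronger readings are tempting but not supported:

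- **Every admission is serious, or forces withdrawal.** Section 7.2 requires an untoward occurrence, so an elective stay need not qualify, and withdrawal is never automatic.
- **A liver-test hold counts as missed doses.** Section 4.4.1 opens a discussion of management "if a patient misses 2 consecutive doses of study medication". Section 5.6 gives holds their own procedure and does not call them missed doses.
- **Off-drug patients may not keep their visits.** The Protocol is silent on this. It neither schedules nor forbids them.
- **The percentages above measure bias in a rate.** They apply to raw counts per patient. With one constant rate for all, a rate per patient-year would not be biased; it would lean low if patients at higher risk leave sooner.

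**Conclusion.** The point holds as a gap in data collection. Section 4.4.1 permits an outcome event to end study participation. Section 5.6 contemplates stopping drug alone. Table 2 footnote b sends those who discontinue early to closing visits without saying whether that means stopping drug or leaving the study. These passages must be reconciled.

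The likely direction is that later hospitalization counts and walk-test means under-represent the sickest patients. The size cannot be derived from the Protocol. The illustrative 4% to 54% of hospitalizations missed per patient depends on assumed rates of 0.2 to 1.0 per year and withdrawal probabilities of 0.1 to 0.5, ignoring death and recovery through later contacts. The walk-test loss is firmer: for withdrawal at Day 100, 400 or 800, 7, 5 or 3 of 8 tests. The effect is confined to descriptive secondary outcomes, so this is an inexpensive improvement and does not undermine the study.

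**What to change.** Leave all clinical grounds for holding or stopping drug as they are, and change only what is collected:

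- **Sections 4.4.1 and 5.6, Table 2 footnote b.** State that stopping drug does not by itself end data collection for a patient who still consents, and say what discontinuing early means in the footnote.
- **Table 1 footnote d, Table 2 footnote b and Section 4.4.2.** Specify that the existing contact or record check records the dates and causes of all hospitalizations and deaths since the last contact, through Day 1344.
- **Walk tests.** Invite consenting off-drug patients who can attend to the 24-weekly 6-MWT visits already scheduled.
- **Section 8.2.4.** Summarize on-drug and off-drug data separately.

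The cost is an amendment to protocol and consent, and some visit or call burden for a few patients. No new procedure is needed. Walk tests will still be missing for those unable to attend, and the report should say how many.

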#### **4.4.2. Handling of Withdrawals**

In the event a patient withdraws or is withdrawn from the study, the Investigator will inform the Medical Monitor at the clinical research organization (CRO) and Alnylam immediately. If there is a medical reason for withdrawal, the patient will remain under the supervision of the Investigator for protocol-specified safety follow up procedures.

When a patient withdraws or is withdrawn from the study, every effort should be made to conduct a complete ET visit as soon as possible following the patient's withdrawal, as described in Table 2.

If a patient is withdrawn for an AE, appropriate medical care should be provided and, if possible, the AE should be followed until resolution.

A patient who fails to return for final evaluations will be contacted by the site in an attempt to have the patient comply with the protocol. The site will follow up by telephone at least twice and send a registered letter to any patient who fails to return for the final evaluation.

When a patient withdraws from the study, the primary reason for discontinuation must be recorded in the appropriate section of the case report form (CRF) and all efforts will be made to complete and report the observations as thoroughly as possible.

For patients who discontinue early and have provided consent, overall health status will be documented by telephone contact or non-patient contact follow-up (eg, medical record check) at the scheduled time points.

#### **4.4.3. Replacements**

No replacements will be allowed for patients who withdraw early from the study.

## **5. STUDY MEDICATION**

### **5.1. Presentation of Study Drug**

The study drug, ALN-TTRSC, is comprised of a siRNA targeting mutant and WT TTR mRNA with a covalently attached triantennary GalNAc ligand formulated in water for injection.

The ALN-TTRSC Solution for Injection will be supplied as a sterile 200 mg/mL solution and packaged in a glass vial. The container closure system consists of a United States Pharmacopeia/European Pharmacopoeia Type I borosilicate glass vial, a Teflon-faced butyl rubber stopper and an aluminum flip-off cap.

### **5.2. Preparation of Study Drug**

The study drug will be prepared by investigational site staff, a healthcare professional, the patient, or caregiver according to the procedures detailed in the Pharmacy Manual.

### **5.3. Storage of Study Drug**

Study drug may be dispensed only by the Investigator, by a staff member specifically authorized by the Investigator, or by a pharmacist, as appropriate. If a patient will receive weekly doses between visits at home, arrangements should be made to allow the required number of vials to be stored either at the site, a homecare health agency, or the patient's home for storage between doses.

All study drug will be stored upright, refrigerated, and protected from light in the storage area of the site pharmacy, homecare health agency, or in a patient's home. Any deviation from the recommended storage conditions should be reported.

No special procedures for the safe handling of ALN-TTRSC are required.

Alnylam, or a designee, will be permitted, upon request, to audit the supplies, storage, dispensing procedures, and records, as applicable.

No study drug may be administered to any person not enrolled in the trial.

Additional storage details are provided in the Pharmacy Manual.

### **5.4. Labeling and Packaging of Study Drug**

All packaging and labeling as well as the preparation of ALN-TTRSC will be in compliance with Good Manufacturing Practice specifications, as described in the Manufacture of Investigational Medicinal Products Volume 4 Annex 13, and any other or local applicable regulations.

Study drug labels for use at study sites will include all appropriate local labeling requirements on the vial and external packaging. Sample labels will be submitted to health authorities, per local country submission requirements.

## **5.5. Dose, Route, and Schedule of Study Drug Measurement of Patient Compliance**

Patients meeting the eligibility criteria will initially receive a daily SC dose of 500 mg of ALN-TTRSC over 5 consecutive days (Days 0, 1, 2, 3, and 4). Doses should be administered 24 ±4 hours apart.

Patients will then receive the same dose of ALN-TTRSC on Day 7 and then weekly from Day 14 through approximately Day1337 (or ET). The Day 7 dose should be administered within ±1 day of the planned dosing date. The weekly doses starting on Day 14 should be administered within ±2 days of the planned dosing date.

Study drug injection during clinic visits will be administered by qualified site staff under the supervision of the Investigator or designee. Dosing after Day 7 may be administered at home by a healthcare professional trained in the protocol, or at the clinic if dosing coincides with the clinic visit for other assessments. The preferred site of injection is the abdomen. Optional additional sites are the upper arms and thighs. The site of injection will be rotated. If a local reaction around the injection site occurs, photographs may be taken.

At the discretion of the Investigator, after the Day 84 dosing visit, and if the patient has not experienced any severe or serious AEs considered related to the study drug within the previous 12 weeks, patients/caregivers may be trained by the Investigator or qualified site staff in the administration of the study drug, according to the protocol dosing requirements. Training of the patient/caregiver in study dosing should be recorded in the site source documentation.

Detailed instructions can be found in the Pharmacy Manual.

## **5.6. Criteria for Dose Interruption, Dose Modification, or Discontinuation of Study Drug**

During the study, if a patient has an elevation of AST, ALT, or total bilirubin (unless due to Gilbert's Syndrome)  $>3 \times \text{ULN}$ , repeat assessments of AST, ALT, and total bilirubin should be performed within 72 hours. The patient should be followed closely, with LFT assessments performed weekly, and as medically indicated to guide patient management. Close monitoring may be discontinued when ALT, AST, and total bilirubin return to  $\leq 3 \times \text{ULN}$ . Additional, and repeat assessments, may be performed at the discretion of the Investigator.

- Dosing will be held for the following liver function test abnormalities: AST or ALT elevation of  $\geq 3 \times \text{ULN}$  in association with either total bilirubin elevation of  $\geq 1.5 \times \text{ULN}$  or gastrointestinal symptoms including nausea, vomiting and/or abdominal pain;
- AST or ALT elevation  $\geq 5 \times \text{ULN}$

Under these circumstances, the Medical Monitor and Investigator will decide on the appropriate action regarding frequency of repeat liver function tests and resumption of dosing.

**Dose-modification criteria:**

If a study drug-related AE occurs in a patient that the Investigator judges as presenting a potential risk to the patient for further dosing, the Medical Monitor and Investigator will review all available safety data for that patient and for all other patients enrolled in the study. Based on this review it may be decided to discontinue further administration of ALN-TTRSC, or, if the Investigator concurs, the patient may resume ALN-TTRSC at the same dose or, at a lower dose of 250 mg.

**Missed doses:**

If a patient misses a dose of study drug and is able to take the dose prior to their next dose, they should receive the missed dose as soon as possible, otherwise the missed dose will not be made up. Patients should never receive more than one dose of study drug a day.

## **5.7. Measurement of Patient Compliance**

Treatment compliance with study drug administration is dependent on the proper preparation and administration of SC injections by study site personnel, the patient's home healthcare professional, or the patient/caregiver who has been trained in study drug administration, as well as attendance by the patient to the clinic. Patients/caregivers will be provided with a diary with which to record study drug administration between clinic visits. Patients will be permitted to miss an occasional dose of study drug. However, if a patient misses 2 consecutive doses, the Investigator, in consultation with the Medical Monitor, will discuss whether the patient will be able to continue on the study.

Patients/caregivers who are administering study drug at home should be instructed to contact the study site if 2 consecutive doses are missed.

